1.8.1.1.6. Overall Number of Days of Occurrence

If a reaction is ongoing at the end of the solicited period, then the overall number of days of presence is derived from the daily intensities and the end date of the reaction after the end of the solicited period. The overall number of days of presence is:

(End date - last vaccination date) + (number of days of presence within the solicited period) - length of the solicited period + 1

If the end date is missing or incomplete (contains missing data), the overall number of days of presence will be considered as Missing.

1.8.1.1.7. Ongoing

Ongoing is derived from the last daily intensity of the solicited period computed as described in [Section 1.8.1.1.1](#) and the maximum intensity on the ongoing period. The investigator's ongoing flag is not used because the measurement would determine the ongoing status of the reaction.

- Ongoing: if the last daily intensity of the solicited period is at least Grade 1 and the maximum intensity on the ongoing period is at least Grade 1
- Not ongoing: if the last daily intensity of the solicited period is None or the maximum intensity on the ongoing period is None.
- Missing: all other conditions (in this case, it is not included in the denominator of the ongoing analysis in the safety tables).

1.8.1.2. Unsolicited AEs

1.8.1.2.1. Presence

An observation will be considered an event if it has at least a verbatim term and is not a Grade 0 intensity event.

Grade 0 events are not included in safety analysis but are included in separate listings.

1.8.1.2.2. Intensity

Intensity will be derived according to the following classification: None, Grade 1, Grade 2, Grade 3, or Missing

If the unsolicited AE is measurable and its preferred term is part of the list of solicited reactions, then the measurement is derived based upon and following the same rule of the intensity scales defined in the protocol for that measurable injection site or systemic reaction. Note the intensity could be considered as "None" (not a reaction) in the analysis despite being considered a reaction by the investigator (e.g., swelling measurement >0 mm but < 25 mm in adults).

Intensity for the other unsolicited AEs will correspond to the value reported in the CRF.

The maximum intensity corresponds to the highest intensity for a unique term.

1.8.1.2.3. Last Vaccination

Last vaccination before an unsolicited AE is derived from the start date of the unsolicited AE provided in the CRF and is calculated as follows:

- If an unsolicited AE has a complete start date and different to any of the vaccination dates, the start date is used to determine the last vaccination before the unsolicited AE
- If the start date is missing or partially missing, or equal to any vaccination date, then the visit number in the “Appeared after Visit” or similar field, is used to determine the last vaccination before the unsolicited AE.

1.8.1.2.4. Time of Onset

Time of Onset = start date of the unsolicited AE - date of last vaccination before the unsolicited AE + 1 (if D1 is the first vaccination day).

The time of onset is considered as missing only if one or both dates are missing or partially missing.

The unsolicited AEs will be analyzed “Within 30 days” after each vaccination, which corresponds to AEs with a time of onset <between 1 and 31 days> or missing / between injection and the next visit or missing (upper limit of the time window of the next visit if visit not done)>. An AE with missing time of onset will be considered to have occurred just after the last vaccination (computed according to the section 3.1.4.2.3), so will be included in these tables.

Time of onset period is displayed as D1-D4, D5-D8, D9-D15, D16 or later, and Missing.

Note: Unsolicited AE that occurred before vaccination (negative time of onset) <or with a time of onset higher than defined above> will not be included in analysis but will be listed separately.

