An unsolicited AE is an observed AE that does not fulfill the conditions of solicited reactions, ie, pre-listed in the CRB in terms of diagnosis and/or onset window post-vaccination. For example, varicella or a solicited term such as headache starting after the solicited observation period (headache starting on D10 post-vaccination in the case where headache occurring between the day of vaccination and the next 7 days is pre-listed in the protocol and CRB as a solicited reaction).

An unsolicited AR is an unsolicited AE that is considered related to study intervention. Unsolicited AEs includes both serious (SAEs) and non-serious unsolicited AEs.

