1.4.4.1.4. Start Date and End Date

Missing or partially missing start dates or end dates for unsolicited AEs (including SAEs) will remain missing and not be imputed. If the start date is missing or partially missing, the time of onset will be considered to be missing. Nevertheless, unsolicited AEs with missing time of onset will be included in analyses according to the last vaccination (computed according to the [Section 1.8.1.2.3](#)). If either the start date or end date is missing or partially missing, the duration will be considered missing.

Missing or partially missing end dates for ongoing solicited AEs will remain missing and not be imputed.

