1.8.1.2.6. Serious Adverse Events

An event will be considered as a serious event if “Yes” is checked for “Serious” in the CRF.

SAEs will be analyzed throughout the study using the following periods:

- Within 7 days after vaccination
- Within 30 days after vaccination
- During the study (i.e., all SAEs occurred during the study)

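### Group 1 SAEs and AESIs from between V2 and V3 that have an incomplete start date are counted as within 30 days of the first booster, even when the known month, year or visit rules that out

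*SAP*

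**What the plan says.** Four SAP rules act together.

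- Section 1.4.4.1.4: "Missing or partially missing start dates or end dates for unsolicited AEs (including SAEs) will remain missing and not be imputed". It continues: "If the start date is missing or partially missing, the time of onset will be considered to be missing". Such events are still analysed: "Nevertheless, unsolicited AEs with missing time of onset will be included in analyses according to the last vaccination".
- Section 1.8.1.2.3 finds that vaccination. For a complete start date that is not a vaccination date, the date itself decides. Otherwise: "If the start date is missing or partially missing, or equal to any vaccination date, then the visit number in the" *Appeared after Visit* field (or a similar one) decides. A known month or year plays no part.
- Section 1.8.1.2.4 confirms that a partial date is enough to make onset missing ("The time of onset is considered as missing only if one or both dates are missing or partially missing"). It then places the event: "An AE with missing time of onset will be considered to have occurred just after the last vaccination". The sentence ends by including the event in the 30-day tables.
- Section 1.8.1.2.6 lists "Within 30 days after vaccination" as one of three periods for SAEs, and 1.8.1.2.7 does the same for AESIs. Neither section has a missing-date rule of its own.

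Protocol 10.2.1 brings SAEs under these rules: "Unsolicited AEs includes both serious (SAEs) and non-serious unsolicited AEs". Protocol 8.3.1 collects non-serious unsolicited AEs from D01 to D31, but SAEs and AESIs throughout the study.

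**The concern.** The rule suits data collected for about a month, where an event of unknown date almost certainly began in the window. Group 1 SAEs and AESIs are different. From V1 until V3 at Year 5 the last study vaccination is the first booster, so an incompletely dated event at any time in those years attaches to that dose and enters its 30-day count.

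The information that would show this to be wrong is often in the database. A known month and year can exclude the window outright. The visit field can nearly do so alone, because V2 falls on Day 31 at the earliest.

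The 30-day SAE and AESI count is what a reader takes as the short-term safety summary of a dose. True counts are likely to be very small, so one misplaced seizure, Kawasaki disease, Guillain-Barré or thrombocytopenic purpura report would change the picture. The effect also falls on one dose only. After the Group 1 second booster and the Group 2 booster, scheduled follow-up ends 30 to 44 days later, so those summaries have no long tail to draw from.

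**Working it through.** The plan gives no figure on this point, so there is none to reproduce. The check traces the rule through an example and then compares the window with the interval.

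**Tracing the rule.** Assume V1 on 1 March 2022 and a Group 1 SAE in June 2024, recorded as appearing after V2.

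1. Complete date, 15 June 2024: onset = 837 + 1 = Day 838. This lies outside Days 1 to 31, so the event is not in the 30-day table.
2. Same event, day unknown: onset is missing (1.4.4.1.4), the last vaccination is V1 (1.8.1.2.3), and the event is in the 30-day table (1.8.1.2.4). Yet the known month alone puts onset between Day 824 (1 June) and Day 853 (30 June).

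The rest of 1.8.1.2.4 does not rescue the case. The section still carries two alternative window definitions in template brackets, and both admit events with missing onset. The exclusion for late onset needs a computed onset, which such an event lacks.

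**Visit field.** V2 is planned at V1 + 30 days with a window of +14 days only (Schedule of Activities, Group 1). An event that appeared after V2 therefore starts on Day 31 at the earliest, and can lie within Days 1 to 31 only if V2 and the onset were both on Day 31.

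**Window against interval.**

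- V1 to V3: 5 years = 1826 days.
- Share inside the window: 31/1826 = 1.7%.
- Days outside: 1826 − 31 = 1795; ratio outside to inside = 1795/31 = 57.9.

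Let s be the share of later SAEs with an incomplete start date. At a constant SAE rate, misplaced events divided by true 30-day events = 57.9 × s. The two are equal at s = 31/1795 = 1.7%.

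For absolute numbers, take 250 children (the plan's maximum for Group 1) and assume 2 SAEs per 100 person-years:

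- True 30-day SAEs: 250 × 31/365.25 × 0.02 = 0.42.
- Later SAEs: 250 × 1795/365.25 × 0.02 = 24.6.

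| s (assumed) | Misplaced / true | Misplaced SAEs |
|---|---|---|
| 0.5% | 0.29 | 0.12 |
| 1% | 0.58 | 0.25 |
| 1.7% | 1.0 | 0.42 |
| 5% | 2.9 | 1.2 |
| 10% | 5.8 | 2.5 |

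With the SAE rate varied from 0.5% to 4% per year and s from 1% to 10%, misplaced SAEs run from 0.06 to 4.9, against 0.11 to 0.85 true ones. Neither the SAE rate nor s comes from the documents. The table shows sensitivity and is not a forecast.

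**The case against.** The strongest reply is that the exposure is narrow.

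- **The first-booster result is first reported without this problem.** Protocol 9.5 and SAP 1.5 set an interim lock and a 5-year report on Group 1 data up to V2. No later SAE can be in it, and a changed count in the final report can be compared with it. This stands: only the final report is exposed.
- **Incomplete SAE dates may be rare.** Group 1 receives a safety diary card at V2, SAEs are reported within 24 hours, the investigator reviews hospital records, and monitors verify source data. This makes a small s plausible. It does not make it zero, and the SAP itself provides for incomplete dates on SAEs.
- **The error is conservative and partly visible.** It adds early events and hides none, and the onset display has a category for missing. Safety is descriptive in an uncontrolled study, so no test is biased. Causality assessment also considers the delay since vaccination. All of this is true, but the events still count in the 30-day total. Conservatism is a reason to include an event when its timing is unknown. It is not one when the recorded data exclude the window.

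A reader might also infer more than the documents support:

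- *That all Group 1 SAEs from Years 1 to 5 enter the 30-day tables.* A complete date gives an onset beyond Day 31, and the event stays out.
- *That every incompletely dated unsolicited AE is placed after a dose.* Group 2 procedure-related SAEs before V2 have no earlier study vaccination to attach to.
- *That the 7-day count is inflated too.* SAP 1.8.1.2.4 ties its rule to the 30-day tables, and 1.8.1.2.6 and 1.8.1.2.7 are silent on missing onset for 7 days. The 7-day treatment is unstated.
- *That the 30-day count will consist mostly of late events.* That needs s above about 1.7%, which the documents neither give nor exclude.

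**Conclusion.** The point holds for Group 1 SAEs and AESIs that start between V2 and V3 and have an incomplete start date. As written, the SAP counts them within 30 days of the first booster even when the known month and year or the visit field contradicts this. It is a stated rule that gives a wrong result, not a missing detail.

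The effect is confined to the final report and overstates early events. Its size cannot be determined from the documents. On the assumption of a constant SAE rate over the five years, the break-even share of incomplete dates is about 1.7%; below it the true 30-day events outnumber the misplaced ones. In absolute terms the numbers are probably small, but so is the true count they would be added to. The change is worth making before the final analysis; it does not call the design or the primary objective into question.

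**What to change.** Amend SAP 1.4.4.1.4 and 1.8.1.2.4 as follows:

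- Count an event with an incomplete start date in the 30-day window only if its known date parts and its *Appeared after Visit* entry are compatible with onset in that window. Otherwise count it under the whole-study period only.
- State the same rule for the 7-day window in 1.8.1.2.6 and 1.8.1.2.7.
- Keep the present conservative rule wherever the window remains possible, for example when no date is known and the visit field points to the vaccination visit.

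Section 1.8.1.2.4 needs editing anyway: its window definition has unresolved template brackets, and it cites a section 3.1.4.2.3 that the SAP does not contain (the rule is in 1.8.1.2.3). The cost is a few sentences and a small programming change. No new data are needed, because the rule uses date parts and a visit field that the SAP already relies on.

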1.8.1.2.5. Duration

Duration is derived from the start and end dates of the unsolicited AE:

Duration = End date of unsolicited AE - start date of unsolicited AE + 1.

The duration is considered as missing only if one or both of the start and end dates of the unsolicited AE is missing or partially missing.

1.8.1.2.6. Serious Adverse Events

An event will be considered as a serious event if “Yes” is checked for “Serious” in the CRF.

SAEs will be analyzed throughout the study using the following periods:

- Within 7 days after vaccination
- Within 30 days after vaccination
- During the study (i.e., all SAEs occurred during the study)

1.8.1.2.7. Adverse Events of Special Interest

An event will be considered as an AESI if “Yes” is checked for “Is the event an AESI?” in the CRF.

AESIs will be analyzed throughout the study using the following periods:

- Within 7 days after vaccination
- Within 30 days after vaccination
- During the study (i.e., all AESIs occurred during the study)

1.8.2. Other Safety Endpoints

1.8.2.1. Pregnancy

This information will not be included in the analysis but will be listed separately. No derivation or imputation will be done.

1.8.2.2. Action Taken

This information will be summarized as collected, including missing observations. No derivation or imputation will be done.

1.8.2.3. Seriousness

This information will be summarized as collected. No derivation or imputation will be done.

1.8.2.4. Outcome

This information will be summarized as collected. No derivation or imputation will be done.

1.8.2.5. Causal Relationship

This information will be summarized as collected in the field “Relationship to study vaccine”. Missing causal relationship will be handled as described in [Section 1.4.4.1.2](#). Relationship to study procedure is only presented in the listing.

1.8.2.6. Adverse Events Leading to Study Discontinuation

This information will be summarized as collected. A flag is available in the clinical database for all AEs in order to identify AEs leading to discontinuation before the end of active phase.

In general, the items that are counted are:

- Disposition table: A participant who, on the “Completion at End of Study” form question “What was the participant's status?” has “Adverse Event” checked.
- Safety overview table: A participant who has either on the “Completion at End of Study” form, question “What was the participant's status?” has “Adverse Event” checked or lists a

solicited AE that has “Caused Study Termination” checked that is at least Grade 1 or an unsolicited AE that has “Caused Study Discontinuation” checked that is at least Grade 1 or missing and is within the time period indicated.

- System Organ Class (SOC)/Preferred Term (PT) table: A solicited AE that has “Caused Study Termination” checked that is at least Grade 1 or an unsolicited AE that has “Caused Study Discontinuation” checked that is at least Grade 1 or missing and is within the time period indicated.

1.8.3. Immunogenicity

1.8.3.1. Computed Values for Analysis

In order to appropriately manage extreme values (undetectable responses $<$ the lower limit of quantitation [LLOQ] and \geq the upper limit of quantitation [ULOQ]) for analysis purposes, the following computational rule is applied to the values provided in the clinical database for each blood sample drawn:

- If a value is $<$ LLOQ, then use the computed value LLOQ/2
- If a value is between \geq LLOQ and $<$ ULOQ, then use the value
- If a value is \geq ULOQ, then use the computed value ULOQ

1.8.3.2. Fold-rise

The derived endpoint fold-rise is driven by both baseline and post-baseline computed values and is computed as follows:

- Calculate the fold-rise of values as the ratio of post-baseline computed value divided by baseline computed value

Note: If baseline or post-baseline is missing, then fold-rise is missing.

1.8.3.3. hSBA Vaccine Seroresponse

The derived vaccine seroresponse indicator for hSBA will be “Yes” if:

- hSBA titer is $<$ 1:8 at baseline with a post-baseline hSBA titer \geq 1:16
- or hSBA titer is \geq 1:8 at baseline with a \geq 4-fold increase at post-baseline

1.8.3.4. rSBA Vaccine Seroresponse

The derived vaccine seroresponse indicator for rSBA will be “Yes” if:

- rSBA titer is $<$ 1:8 at baseline with a post-baseline rSBA titer \geq 1:32
- or rSBA titer is \geq 1:8 at baseline with a \geq 4-fold increase at post-baseline

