
Immunogenicity
 
 • To describe the antibody persistence of meningococcal serogroups A, C, W, and Y in children who received MenACYW conjugate vaccine approximately 5 years earlier as toddlers (Groups 1 and 2) • To describe the antibody persistence of meningococcal serogroups A, C, W, and Y in adolescents who received MenACYW conjugate vaccine approximately 10 years earlier as toddlers (Group 2) • To describe the antibody persistence of meningococcal serogroups A, C, W, and Y in adolescents who received a booster as children approximately 5 years after the primary dose of MenACYW conjugate vaccine as toddlers (Group 1) • To describe the antibody responses to meningococcal serogroups A, C, W, and Y before and 30 days after the administration of a booster dose of MenACYW conjugate vaccine in children who received MenACYW conjugate vaccine approximately 5 years earlier as toddlers (Group 1) • To describe the antibody responses to meningococcal serogroups A, C, W, and Y before and 30 days after the administration of a booster dose of MenACYW conjugate vaccine in adolescents who received MenACYW 	
Immunogenicity
 
 • Antibody titers² against meningococcal serogroups A, C, W, and Y measured by hSBA and rSBA at V1 (baseline) for Group 1 and Group 2 • Antibody titers² against meningococcal serogroups A, C, W, and Y measured by hSBA and rSBA at V2 (Group 2) • Antibody titers² against meningococcal serogroups A, C, W, and Y measured by SBA and rSBA at V3 (Group 1) • Antibody titers² against meningococcal serogroups A, C, W, and Y measured by hSBA and rSBA at V1 (baseline) and V2 (30 days after the administration of a booster dose of MenACYW conjugate vaccine) (Group 1) • Antibody titers² against meningococcal serogroups A, C, W, and Y measured by hSBA and rSBA at V2 and V3 (30 days after the administration of a booster dose of MenACYW conjugate vaccine) (Group 2) • Antibody titers² against meningococcal serogroups A, C, W, and Y measured by hSBA and rSBA at V3 and V4 (30 days after the administration of a booster dose of MenACYW conjugate vaccine) (Group 1) • Antibody concentrations against tetanus toxoid at V1 (baseline) and V2 (30 days after the administration of a 5-year booster dose of MenACYW conjugate vaccine) (Group 1)

Objectives	Endpoints

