1.3. Populations for Analyses

The following populations are defined:

Population	Description
Study participants with data in CRF Error! No document variable supplied.	All study participants included in the table shells are study participants with a Case Report Form (CRF) (i.e., with data in the clinical database).
Safety Analysis Set (SafAS)	
SafAS 1: Participants who have received the study vaccine 5 years after priming vaccination (at V1) and have any safety data available (Group 1).
 
SafAS 2: Participants who have received the study vaccine 10 years after priming vaccination at V3 (Group 1) / V2 (Group 2) and have any safety data available.
 
SafAS: Participants who have received at least one dose of the study vaccine. All participants will have their safety analyzed after any dose according to the vaccine received at the 1st dose.
 
All participants will have their safety analyzed according to the vaccine scheme they actually received.
 
Safety data recorded for a vaccine received out of the protocol design will be excluded from the analysis (and listed separately).

Full analysis set (FAS)	
The FAS will be duplicated for each FAS defined below: 1 each for hSBA and rSBA measurements.
 
FAS1: Subset of participants who received the study vaccine and had a valid post-vaccination serology result (hSBA or rSBA accordingly) 5 years after priming vaccination at V1 (Group 1). Participants will be analyzed according to the intervention they received.
 
FAS2: Subset of participants who received the study vaccine and had a valid post-vaccination serology result (hSBA or rSBA accordingly) 10 years after priming vaccination at V3 (Group 1) / V2 (Group 2). Participants will be analyzed according to the intervention they received.
 
FAS3: For persistence includes participants who had a valid baseline serology result (hSBA or rSBA accordingly) (5-year antibody persistence, Group 1 and Group 2)
 
FAS4: For persistence includes participants who had a valid pre-vaccination serology result (hSBA or rSBA accordingly) (5-

	
year antibody persistence after the first booster dose in Group 1, 10-year antibody persistence in Group 2). Participants will be analyzed according to the intervention they received.

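### Does the undefined 'baseline' in the SAP's fold-rise and seroresponse rules put the wrong reference sample under the Year 5 boosters?

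*SAP*

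**What the plan says.** The derivation rules are generic. SAP 1.8.3.2 says to "Calculate the fold-rise of values as the ratio of post-baseline computed value divided by baseline computed value", and its note adds "If baseline or post-baseline is missing, then fold-rise is missing". The hSBA seroresponse rule in 1.8.3.3 follows the same pattern ("1:8 at baseline with a post-baseline hSBA titer"), and so does the rSBA rule in 1.8.3.4. None of the three names a visit or says that it is applied dose by dose.

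Elsewhere the SAP is specific. Table 2.1 lists titers "measured by hSBA and rSBA at V1 (baseline) for Group 1 and Group 2". For the Year 5 doses it lists titers "measured by hSBA and rSBA at V3 and V4 (30 days after the administration of a booster dose of MenACYW conjugate vaccine) (Group 1") and "measured by hSBA and rSBA at V2 and V3 (30 days after the administration of a booster dose of MenACYW conjugate vaccine) (Group 2"). Its footnote says that these titers will be reported as seroresponse, among other measures. SAP 1.4.3 and protocol 9.4.3.1 define the 4-fold rise and the hSBA and rSBA seroresponses by comparing the titer after vaccination with the titer before it.

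In SAP 1.3, the 5-year persistence set uses the word baseline ("FAS3: For persistence includes participants who had a valid baseline serology result"), while FAS4, the Year 5 counterpart, refers to the pre-vaccination result. The set behind the Year 5 response analyses asks only for a post-dose result ("FAS2: Subset of participants who received the study vaccine and had a valid post-vaccination serology result").

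**The concern.** Group 1 receives two study doses. Group 2 receives its only study dose 60 months after V1. For the Year 5 doses, baseline could therefore mean V1 or the sample drawn just before the injection.

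Wherever the SAP attaches the word to a serology visit, that visit is V1, even for Group 2, which is not vaccinated then. The Year 5 pre-dose sample is never called baseline. A programmer who worked from 1.8.3 alone and carried over that usage would compare V4 (Group 1) or V3 (Group 2) with V1.

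In Group 1, the response to the second booster would then include whatever remained of the first. In Group 2, the response to the 10-year booster would look weaker if titers had fallen between V1 and V2. The missing-value note would also discard a complete pre-dose and post-dose pair whenever the V1 result was absent.

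**Working it through.** **1. Primary objective.** Inputs from SAP 1.2: n = 84, null proportion 0.75, one-sided alpha 0.025, exact test. The smallest count whose Clopper-Pearson lower 97.5% limit exceeds 0.75 is 72 of 84 (limit 0.7638; 71 gives 0.7499). Power is the probability of at least 72 responders:

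| Serogroup | Assumed rate | Power | Stated |
|---|---|---|---|
| A, Y | 0.95 | 99.97% | > 99.9% |
| W | 0.925 | 99.03% | 99.0% |
| C | 0.90 | 92.59% | 92.6% |

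The product over the four serogroups is 91.6%, against a stated global power above 90%. The endpoint runs from V1 to V2 in Group 1, where V1 is both the baseline and the pre-dose sample. The wording question therefore cannot move any of these figures.

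**2. What the choice of reference does to one participant.** For hSBA, a reference below 1:8 requires at least 1:16; otherwise at least 4 times the reference is required. The patterns below are chosen to show the mechanism and are not data.

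- Group 1, V1 = 1:4, V3 = 1:32, V4 = 1:64. The cut-off is 1:16 against V1 and 4 × 32 = 128, so 1:128, against V3. The fold-rise is 64/4 = 16 (seroresponse) or 64/32 = 2 (none).
- Group 2, V1 = 1:32, V2 = 1:4, V3 = 1:64. The cut-off is 4 × 32 = 128, so 1:128, against V1 and 1:16 against V2. The fold-rise is 64/32 = 2 (none) or 64/4 = 16 (seroresponse).

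So the reference can matter for an individual, in either direction. The population effect cannot be computed, because the documents give no Year 5 titers.

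**3. Which reference the plan supports.**

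| Place | What it implies for the Year 5 doses |
|---|---|
| SAP 1.8.3.2 to 1.8.3.4 | No visit named |
| SAP 1.4.3 | Pre-vaccination to post-vaccination, after listing the Year 5 visits of both groups |
| Protocol 9.4.3.1 | The same |
| SAP Table 2.1 | V3 with V4 (Group 1), V2 with V3 (Group 2); V1 is in neither pair |
| SAP section 4, introduction | The section containing 1.8.3 supplements the protocol |
| Protocol section 9 | The SAP is to follow the protocol |
| SAP section 5 | No changes to planned analyses |

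The first row is silent and the rest fit the pre-dose sample. Measuring Year 5 seroresponse from V1 would depart from protocol 9.4.3.1, and section 5 declares no departure.

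**4. Does the V1 reading work on its own terms?** Post-baseline is undefined too. If baseline is V1 throughout, then V2 in Group 2 is a post-baseline sample, and the rule would return a vaccine seroresponse before that group had received any study vaccine. The rule makes sense only when applied around each dose.

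**5. Missing values.** Applied per dose, the note concerns V3/V4 or V2/V3, and a missing V1 result is irrelevant. A V1 blood sample is in any case scheduled for every participant in both groups.

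**The case for a change.** The best argument for a change is that 1.8 is the SAP's calculation section, where a programmer would naturally look. Its safety part handles repeated doses properly, by defining the last vaccination and counting onset from it; its immunogenicity part has no equivalent. The split in vocabulary between FAS3 and FAS4 belongs to the SAP, since the protocol calls both samples pre-vaccination. No sentence states outright which text prevails, and the introduction to section 4 is not a formal precedence clause.

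All of that is accurate, and naming the visit pairs would have been tidier. It does not make the plan contradictory. The rule in 1.8.3 conflicts with 1.4.3 only once a visit label is imported from the endpoint table, and that same table gives the correct pairs for the Year 5 doses. In the Group 1 rows that pair V1 with V2, V1 is itself the pre-dose sample, so the label there is consistent with the per-dose reading.

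Simulated effects do not strengthen the objection. Every mean, spread and correlation would have to be assumed, and the size of the result would follow from those assumptions.

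**Conclusion.** No change is needed. The terms are undefined in 1.8.3.2 to 1.8.3.4, but the pre-vaccination definitions in both documents and the visit pairs in SAP Table 2.1 supply the meaning: V1/V2 and V3/V4 in Group 1, V2/V3 in Group 2. Under that reading there is no error in any output.

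Even if the terms were misread, the exposure would be limited to descriptive fold-rise and seroresponse percentages after the Year 5 doses, with no hypothesis tested. The primary test, its power, the 5-year report, GMTs, seroprotection rates and distribution curves would stand. Titers at both visits of each pair are reported alongside, which would help reveal a wrong reference.

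The conclusion assumes that the analyst reads 1.8.3 together with 1.4.3 and Table 2.1. That is reasonable, since 1.8.3 alone does not say which samples to use for any dose.
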